7.1. Study Design

Patient is identified and consent is obtained in clinic, hospital room or pre-operative area. In the Same Day Pre-Anesthesia Care Unit they will receive Robitussin DM 20 ml syrup orally (Dextromethorphan 20mg) at least 60 minutes prior to bronchoscopy.

Once in the main procedure room patients will be induced into an anesthetic state using the following medications and dosing ranges. It will be titrated by anesthesiologist at bedside with goal to achieve hypnosis and apnea without profound bradycardia. The duration of the infusion is as required for the duration of the procedure.

- Propofol (1-3 mg/kg bolus and infusion of 50-200 mcg/kg), fentanyl 25-50 mcg on induction and alfentanil as a continuous infusion will be given at a rate of 0.5-2 mcg/kg/min with 1-3 mcg/kg bolus every 2-5min if need for further cough suppression. The Propofol infusion will be titrated to maintain BIS values between 40-60 for the duration of the procedure. When it is anticipated that the procedure will conclude within the next 10 minutes, the Propofol and alfentanil infusions will be stopped.

Contingency Plan: If despite the maximum dose of Propofol (150 mcg/kg/min) and alfentanil the patient continues to cough such that the procedure cannot be carried out, then Rocuronium will be administered IV (dose 20-40 mg at the discretion of the anesthesiologist) and its residual effect will be reversed using neostigmine (20-70 mcg/kg) and glycopyrrolate (10 mcg/kg) at the end of the procedure.

The patient's airway will be managed using a laryngeal mask airway (LMA) (Ambu Aura-I Size 4 or 5). Their airways will be anesthetized using a maximum of 2 mg per kg (max dose 160mg) of lidocaine, administered by one of the following techniques below. Randomization will be completed by selection of unmarked envelope.

- 1. "Spray as you go" 16mL of 1% lidocaine sprayed in 4 mL aliquots. One at the vocal cords, one at midtrachea, one at left main stem bronchus and one at right mainstream bronchus.

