- 2. Nebulizer 2 % (preservative free) lidocaine (dose 2mg/kg max dose 160 mg) will be administered via a jet nebulizer, in the operating room over ten minutes, followed by procedure immediately after. The patient will be sitting propped up and his SpO2, EKG and BP will be monitored during this time. The jet nebulizer supply tube will be connected to central oxygen at 6 L/min and the duration of nebulization will be dryness of the nebulizing chamber or max of 10 minutes. [The Salter Series Small Volume Jet Nebulizer will be used.]
- 3. Vibrating Mesh Nebulizer 2 % (preservative free) lidocaine (dose 2mg/kg max dose 160 mg) will be administered via a vibrating mesh nebulizer, in the operating room over ten minutes, followed by procedure immediately after. The patient will be sitting propped up and his SpO2, EKG and BP will be monitored during this time. The jet nebulizer will be

connected to central oxygen at 6 L/min and the duration of nebulization will be dryness of the nebulizing chamber or max of 10 minutes. [The Aerogen Solo Vibrating Mesh Nebulizer will be used.]

Patient will undergo scheduled procedure of flexible bronchoscopy or endobronchial ultrasound examination. During procedure, bronchoscopist and anesthesiologist will count the number of episodes of cough. Cough is defined as a cough which requires intervention such as additional dose of anesthetic or requires a pause in the procedure. During procedure, BIS monitor average, number of vasopressor interventions for MAP <60, induction time, procedure time and wake up time will be documented in the research record.

Following procedure, patient will be brought to post-op anesthesia care unit. Time to discharge readiness will be collected as well as the responses of the patient to the following questions:

- sore throat: absent, mild, moderate, severe
- cough: absent, mild, moderate, severe

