7.4.2. Treatment Regimen

Their airways will be anesthetized using 160mg of lidocaine, administered by one of the following techniques:

- 1. "Spray as you go" 16mL of 1% lidocaine sprayed in 4 mL aliquots. One at the vocal cords, one at midtrachea, one at left main stem bronchus and one at right mainstream bronchus.
- 2. Jet Nebulizer 8 mL of 2 % lidocaine administered via a jet nebulizer over ten minutes, followed by procedure immediately after.
- 3. Vibrating Mesh Nebulizer 8 mL of 2 % lidocaine administered via a vibrating mesh nebulizer over ten minutes, followed by procedure immediately after.

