7.4.6. Receiving, Storage, Dispensing and Return

7.4.6.1. Receipt of Test Article

Lidocaine will be ordered from the pharmacy. The vibrating mesh nebulizer and jet nebulizer will be set up by anesthesiologist and spray as you go will be set up by OR staff and bronchoscopist.

7.4.6.2.Storage

Same medication obtained from pharmacy is used across all three groups, the mode of administration is only part changed and will be completed by anesthesiologist and/or bronchoscopist.

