10.8. Suspension of research

Will be based on safety data collection following each subject's bronchoscopy.

11. Risks

There is the potential risk of loss of confidentiality with this study due to consent being required however no personal identifiers will be attached to the data we collect. There is no other forseeable risk to the patients involved in this study. All medications and procedures fall within standard treatment and standard of care. The only variable will be the delivery method of the medication used during bronchoscopy. There is no risk to the researchers or hospital staff either. Loss of confidentiality is always a potential risk, but no protected health information will be maintained or collected, minimizing this risk. Risk of randomization is also present however all modalities are considered standard of care.

12. Potential Benefits to Subjects and Others

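### The lidocaine dose rules in 7.1 and 7.4.2 conflict below 80 kg, and spray differs from the nebulizers in concentration as well as mode

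*Combined protocol and SAP*

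**What the plan says.** Section 7.1 opens its lidocaine paragraph with a limit that covers every technique listed after it: "Their airways will be anesthetized using a maximum of 2 mg per kg (max dose 160mg) of lidocaine". The spray item then gives a volume and no per-kilogram dose: "16mL of 1% lidocaine sprayed in 4 mL aliquots". The jet item restates the weight-based dose: "2 % (preservative free) lidocaine (dose 2mg/kg max dose 160 mg) will be administered via a jet nebulizer". The mesh item has the same concentration and dose. Both nebulizer items carry the same stop rule: "the duration of nebulization will be dryness of the nebulizing chamber or max of 10 minutes".

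Section 7.4.2 has no weight-based limit: "Their airways will be anesthetized using 160mg of lidocaine, administered by one of the following techniques". It gives spray the same 16 mL of 1% and each nebulizer 8 mL of 2%; for mesh it reads "8 mL of 2 % lidocaine administered via a vibrating mesh nebulizer over ten minutes".

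Two other places describe what differs between arms. Section 7.4.6.2 (Storage) says: "Same medication obtained from pharmacy is used across all three groups, the mode of administration is only part changed". Section 11 (Risks) says: "The only variable will be the delivery method of the medication used during bronchoscopy".

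**The concern.** Staff treating a patient under 80 kg have two sections to follow, and these give different doses. Which one they follow decides whether the patient stays within the protocol's own limit, and whether spray and nebulizer patients of the same weight are loaded with the same amount of drug.

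Interpretation is also at stake. The study looks for a difference between topical and nebulized lidocaine and, if it finds one, will use it to size a superiority trial (2.3). If spray and nebulizer differ in concentration, and possibly in loaded dose, a difference in severe cough cannot be credited to mode of delivery alone.

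**Working it through.** **Inputs.** All come from 7.1 and 7.4.2: spray 16 mL of 1%; nebulizers 2%, at 2 mg/kg up to 160 mg (7.1) or 8 mL (7.4.2); overall cap 2 mg/kg, maximum 160 mg (7.1). Conversions: 1% = 10 mg/mL and 2% = 20 mg/mL.

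**The plan's own figure.** Spray: 16 mL × 10 mg/mL = 160 mg. Nebulizer: 8 mL × 20 mg/mL = 160 mg. The 160 mg in 7.4.2 reproduces in every arm.

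**Where the cap binds.** 2 mg/kg × weight = 160 mg at 160/2 = 80 kg. Below that weight, 160 mg is over the cap.

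**Size by weight.**
- Fixed dose per kg = 160/weight.
- Capped load = min(2 × weight, 160) mg.
- Ratio = 160/capped load. The excess over the cap is this ratio minus 1.
- Capped spray volume = capped load/10, divided by 4 for each aliquot.

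| Weight | Fixed 160 mg, per kg | Excess over 7.1 cap | Nebulizer load in 7.1 | Spray/nebulizer ratio, 7.1 line by line | Spray volume if capped (per aliquot) |
|---|---|---|---|---|---|
| 50 kg | 3.20 mg/kg | 60% | 100 mg (5 mL) | 1.60 | 10 mL (2.5 mL) |
| 60 kg | 2.67 mg/kg | 33% | 120 mg (6 mL) | 1.33 | 12 mL (3.0 mL) |
| 70 kg | 2.29 mg/kg | 14% | 140 mg (7 mL) | 1.14 | 14 mL (3.5 mL) |
| 80 kg | 2.00 mg/kg | 0% | 160 mg (8 mL) | 1.00 | 16 mL (4.0 mL) |

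Above 80 kg every arm is at 160 mg and the ratio stays at 1.00.

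**Three readings below 80 kg.**
1. Each item of 7.1 is followed as written. Spray gets 160 mg and the nebulizers 2 mg/kg. Loads differ by the ratios above, and spray exceeds the cap.
2. The opening sentence of 7.1 governs spray, so 16 mL is a ceiling. All arms get 2 mg/kg and loads are equal. Section 7.4.2 is then not followed.
3. Section 7.4.2 governs. All arms get 160 mg and loads are equal. Every arm then exceeds the 7.1 cap by the percentages above.

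No reading satisfies both sections below 80 kg.

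**Concentration.** Spray is 1% in both sections, and both nebulizers are 2% in both. At equal mass, spray therefore uses twice the volume at half the strength. This holds at every weight and contradicts the statements in 7.4.6.2 and section 11 for spray versus nebulizer. Jet and mesh share concentration, dose rule and stop rule, so the device is the only stated difference between them.

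**The case against.** The best defence of 7.1 is that its opening sentence applies to every technique listed below it, and spray is the first. Read that way, 16 mL is the ceiling volume and 7.1 is consistent with itself. This is a fair reading, and it means that unequal loads are possible but not established. It does not reconcile 7.1 with 7.4.2, which gives a flat 160 mg and no limit per kilogram.

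On concentration, the plan matches nominal drug mass at 160 mg, and strength can be seen as part of each delivery regimen. The two statements about mode sit under Storage and Risks, where they describe supply and reassure about risk; neither is an analysis claim. The planned analysis is descriptive (8.3, 10.7). All of this stands, and it limits the consequence to wording and interpretation. The statements are still inaccurate for spray versus nebulizer.

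A reader might go further in three ways, none of which the documents support:
- **Nebulized patients are under-dosed by the 10-minute limit.** Emptying 8 mL in 10 minutes needs 0.8 mL/min. The documents give no device output, so any shortfall is unknown and may be zero.
- **Lidocaine given is not captured.** The data items in 7.1 and 16.1 do not name it, but the general items on anesthetic amount (2.3, 16.1) could include it. The subject form and the data plan form are not among the documents.
- **The primary comparison is biased.** Patients are randomised to regimens, and these differences belong to the regimens. The comparison of the regimens as used is not biased by them.

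**Conclusion.** The dose rules are wrong as written: below 80 kg, 7.1 and 7.4.2 cannot both be followed. A fixed 160 mg is 60%, 33% and 14% over the 7.1 cap at 50, 60 and 70 kg. The conflict itself rests on no assumption beyond the stated doses. The load ratios of 1.60, 1.33 and 1.14 apply only if 7.1 is followed item by item; under the other two readings they are 1.00. The documents give no weight distribution, so the number of the 48 patients below 80 kg is unknown. The excess is measured against the protocol's own limit, and the documents do not show that it would cause harm.

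The 1% versus 2% difference is certain. It narrows what can be said about mode in the spray versus nebulizer comparison. It does not touch jet versus mesh.

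**What to change.** State one lidocaine dose rule, in the same words, in 7.1 and 7.4.2. Which rule to adopt is the investigators' clinical choice. If the 7.1 cap is kept:
- all arms get 2 mg/kg up to 160 mg;
- spray is 2/10 = 0.2 mL/kg of 1%, maximum 16 mL, in four equal aliquots;
- nebulizers get 2/20 = 0.1 mL/kg of 2%, maximum 8 mL.

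If the flat 160 mg is kept, remove the per-kilogram limit from 7.1.

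Correct 7.4.6.2 and section 11, and describe spray versus nebulizer as a comparison of delivery regimens that also differ in concentration. Record body weight and lidocaine given (mg) for all 48 patients, if the forms do not already do so. Nebulization time and residual volume for the 24 nebulizer patients are optional extras.

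The cost is one aligned dose rule, two wording corrections and two form fields. Under the capped rule, lighter spray patients get smaller aliquots (2.5 mL each at 50 kg instead of 4 mL), which may change how the spray covers the airway. The claim about mode also becomes narrower.

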1.2. Primary Study Endpoints

The primary endpoint will assess if different modes of lidocaine administration ("spray as you go" vs nebulized vs atomized) decrease the severity of intraoperative coughing. Severe coughs will be identified by the anesthesiologist and bronchoscopist as cough which results in pausing procedure and/or requiring repeated dosing of anesthetic.

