1.3. Secondary Study Endpoints

Secondary endpoints will include: additional amount(s) of fentanyl and propofol used to suppress cough during procedure, cough and sore throat post-procedure and time to emergence following the end of the procedure.

2. Background

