2.3. Study Rationale

While the procedures of flexible bronchoscopy and endobronchial ultrasound is commonly performed to assess a wide range of lung disease, studies evaluating the mode of administration of topical lidocaine to prevent coughing and improve efficiency of the procedure have not yet been completed. We propose a prospective, randomized, stratified sampling, open label study of topical vs nebulized vs atomized lidocaine during flexible bronchoscopy and endobronchial ultrasound. Postoperative outcome assessors will be blinded to intraoperative therapy. We propose to evaluate the different modes of administration of topical lidocaine and their effect on the number of severe coughs as per anesthesia and the bronchoscopist, total dosing of anesthesia, post-procedure cough and sore throat and complications related to lidocaine.

As there have been no studies in regards to the mode of lidocaine application in bronchoscopy, our study is a feasability study to identify if a difference is present between nebulized and topical groups. If one is identified, we will plan to determine number needed to power a future superiority study.

Inclusion and Exclusion Criteria

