3.2. Exclusion Criteria

The following exclusion criteria will be used:

- 1. Any intervention beyond flexible bronchoscopy and EBUS/TBNA
- 2. Inability to tolerate bronchoscopy.
- 3. Patients that receive paralytics.
- 4. Patients with neuromuscular diseases.
- 5. Inability to consent for procedures.
- 6. Allergies to lidocaine or any other drugs used in protocol.
- 7. Existing renal insufficiency or liver disease

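### The primary measure is a raw cough count in which rocuronium rescue, the clearest failure of cough control, is never counted as a failure

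*Combined protocol and SAP*

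**What the plan says.** Section 1.2 asks whether the mode of lidocaine administration will "decrease the severity of intraoperative coughing". It defines a severe cough as "cough which results in pausing procedure and/or requiring repeated dosing of anesthetic". It gives no severity grade and no summary variable.

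Elsewhere the measure is a number. Section 2.3 will evaluate the modes and "their effect on the number of severe coughs as per anesthesia and the bronchoscopist", section 7.1 says that the "bronchoscopist and anesthesiologist will count the number of episodes of cough", and section 16.1 lists the number of severe coughs. None of these divides the count by time at risk.

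The contingency plan in section 7.1 applies when the drug doses have reached their maximum: if "the patient continues to cough such that the procedure cannot be carried out, then Rocuronium will be administered IV". At the end of the procedure, "its residual effect will be reversed using neostigmine" and glycopyrrolate.

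Two other places bear on these patients:
- Exclusion criterion 3 in section 3.2 reads "Patients that receive paralytics".
- The withdrawal criteria in section 3.3.1 name early termination for safety and withdrawn consent. They do not name use of a paralytic.

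The secondary endpoints in section 1.3 cover additional fentanyl and propofol, post-procedure cough and sore throat, and "time to emergence following the end of the procedure". Relaxant use is not among them, nor among the items section 7.1 says will be documented. Section 16.1 lists the amount of anesthesia, but no relaxant, time or reason. Sections 8.3 and 10.7 plan medians, interquartile ranges and percentages only.

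**The concern.** By design, rocuronium goes to the patients whose cough was least controlled. Once relaxed, such a patient can add few further episodes, so the count stops rising when topical anesthesia has most clearly failed. A patient who coughs at a moderate rate throughout keeps accruing episodes and may finish with the higher, and so worse, score.

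If rescued patients are instead removed under exclusion criterion 3, the worst coughers leave the comparison because of their outcome, possibly in unequal numbers per arm.

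Section 2.3 says that if a difference is identified, it will be used to determine the number needed for a superiority study. A difference hidden by the scoring could end that programme, and a shrunken one could distort its sizing. With 12 patients in each nebulizer arm (section 8.1), a few such patients carry weight.

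Time to emergence is affected too. It starts at the end of the procedure, when the reversal drugs are given, and nothing marks the patients who received relaxant and reversal.

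**Working it through.** **1. What can be checked against the plan.** The only relevant figure is the sample size: 24 + 12 + 12 = 48, which agrees with section 8.1. Section 8.2 marks the sample size determination as not applicable. The documents give no cough rate, procedure length, rescue rate or time to rescue. Every such input below is assumed.

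**2. The two readings side by side.**

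| Reading of exclusion criterion 3 | Rescued patient's score | Consequence |
|---|---|---|
| Applies at enrolment only | Count up to rescue, little added after | Failure scored as a shortened count |
| Applies after randomization | None | Failure removed from the comparison |

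Neither reading counts rescue as a failure. This step needs no assumed rate.

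**3. Can a rescued patient score lower than a never-rescued one?** Assume no cough after rocuronium. Let the rescued count be R = 1 + Poisson(0.4 × t), with 0.4 coughs per minute until rescue at t minutes. Let the never-rescued count be M = Poisson(r × T), with r coughs per minute over a procedure of T minutes. Then P(R < M) = Σ P(R = k) × P(M > k).

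| T (min) | r (per min) | Mean of M | t = 5, mean R 3.0 | t = 10, mean R 5.0 | t = 15, mean R 7.0 |
|---|---|---|---|---|---|
| 30 | 0.10 | 3.0 | 0.40 | 0.17 | 0.06 |
| 30 | 0.15 | 4.5 | 0.65 | 0.36 | 0.17 |
| 45 | 0.10 | 4.5 | 0.65 | 0.36 | 0.17 |
| 45 | 0.15 | 6.75 | 0.87 | 0.65 | 0.41 |

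The reversal is possible. Its frequency runs from 0.06 to 0.87 over these assumptions.

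**4. Arms that differ only in rescue.** Assume a 40-minute procedure, 0.1 coughs per minute if never rescued (mean 4.0), and rescue at 8 minutes with 0.4 per minute before it (mean 1 + 0.4 × 8 = 4.2). Compare topical with pooled nebulized patients by the probability that a topical patient scores worse, ties counted half. Never-rescued patients are alike in both arms. Excluding the rescued therefore gives 0.50, and ranking rescue worst gives (1 + q1 − q2)/2, where q1 and q2 are the rescue proportions.

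| Rescue, topical v nebulized | Raw count | Rescued excluded | Rescue ranked worst |
|---|---|---|---|
| 30% v 10% | 0.51 | 0.50 | (1 + 0.20)/2 = 0.60 |
| 40% v 10% | 0.51 | 0.50 | (1 + 0.30)/2 = 0.65 |

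Here the raw count and the exclusion both miss the difference.

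**5. Rescue that depends only on the count.** Assume negative binomial counts with means 4 and 2 (shape 1 or 2) and a chance q of rescue at each cough from the third on. The score is the smaller of the full count and 2 + Geometric(q).

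| | No truncation | q = 0.2 | q = 0.4 |
|---|---|---|---|
| Rescued, worse arm v better arm | none | 28–30% v 12–13% | 39–44% v 19–20% |
| Difference in means | 2.0 | 1.1–1.3 | 0.8–1.0 |
| Population medians | 3 v 1–2 | unchanged | unchanged |
| P(worse arm scores higher), shape 1 | 0.64 | 0.63 | 0.63 |
| P(worse arm scores higher), shape 2 | 0.69 | 0.68 | 0.67 |

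At about 10% v 4% rescued, the difference in means is about 1.7. With 24 per group, the average difference in sample medians falls from 1.43 to 1.20–1.24 (shape 1) or from 1.71 to 1.30–1.38 (shape 2). Ranking rescue worst recovers almost nothing in this model, because rescue carries no information beyond the count.

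**The case against.** Exclusion criterion 3, read literally, removes rescued patients. Nobody would then be mis-ranked, and the fault would be outcome-dependent exclusion. That is a fair reading, but section 3.3.1 does not list paralytic use as a ground for withdrawal, and section 7.1 manages the rescued patient to the end of the procedure. The documents leave the matter open, and failure goes uncounted on either reading.

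A reader might infer that one bout of coughing leading straight to rocuronium would score 1, the same as a brief pause. The documents do not support this as the usual course. Rocuronium follows maximum propofol and alfentanil, with alfentanil boluses for cough before that, and each cough that needs a dose or a pause counts. A rescued patient will usually have accrued several episodes.

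A reader might also infer that the measured effect will be cut by half or more. That rests on assumed rescue rates and on means, whereas the plan reports medians. In the model of step 5 the population medians do not move. Nor do the documents give the relaxant's duration or the procedure length, so the assumption of no cough after rescue is untested.

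Finally, this is a 48-patient feasibility study with no test, and the anesthesia record would be expected to show rocuronium use. This limits the consequence. It does not supply a scoring rule, and section 21.1 says that data will not be stored once the study is completed, so rescue is best captured on the form from the start.

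**Conclusion.** The point holds in a limited form. The endpoint is severity and the measure is an unadjusted count. Rescue goes to the patients with the least controlled cough, and the plan never counts it as failure, whether those patients are kept or dropped. That follows from the text alone.

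The effect on the arm comparison could be material where rescue marks a severity that the count does not show (0.51 against 0.60 or 0.65 in step 4). It may be small for medians where rescue is rare or depends only on the count (step 5). The documents cannot say which applies. They therefore do not support a claim that the planning effect for the superiority study would be too small, only that it could be. The change is worth making because it is cheap and the result is meant to inform that study.

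**What to change.** - Reconcile sections 3.2 (criterion 3), 3.3.1 and 7.1 on whether a patient given rocuronium for cough stays in the study. Analyse all randomized patients.
- Add rocuronium use, time and reason to the subject form.
- Report the proportion rescued by arm.
- In sections 1.2 and 8.3, define the primary outcome as an ordered score. Rescue for cough ranks worst, and other patients are ranked by number of severe coughs. Report the plain count, and the count per minute up to rescue, alongside.
- Report time to emergence with relaxant and reversal cases marked.

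The cost is a few form fields, a sentence in each of sections 1.2 and 8.3, and the reconciliation of three sections. The planned medians still apply to an ordered score. The small downside is that the primary summary is no longer a plain count. No change to the clinical contingency rule is proposed.

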3.1. Inclusion Criteria

The following inclusion criteria will be used:

- 1. Diagnosis of mediastinal and/or hilar lymphadenopathy requiring endobronchial ultrasound evaluation and transbronchial needle aspiration.
- 2. Diagnosis of pulmonary disease requiring flexible bronchoscopy
- 3. Greater than 18 years of age.

Vulnerable populations as identified in HRP-412, HRP-413, HRP-414, HRP-415, HRP-416 and HRP-417 will not be included in this study.

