16.1. Facilities and locations

Pre-anesthesia care unit, floor room or interventional pulmonology clinic where consent process will take place.

Pre-anesthesia care unit where patient will receive dextromethorphan.

Main Procedure Room 1 where lidocaine will be administered and procedure completed. Will collect number of severe coughs, amount of anesthesia, time of procedure and wake up time.

Post-anesthesia care unit where time to discharge readiness, patient cough severity and sore throat severity will be collected.

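### Post-procedure cough is rated only in recovery, with no baseline rating described, so pre-existing cough cannot be separated from new or worsened cough

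*Combined protocol and SAP*

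**What the plan says.** Section 1.3 lists among the secondary endpoints "cough and sore throat post-procedure and time to emergence following the end of the procedure". Section 7.1 places the assessment after transfer to the recovery unit: "Time to discharge readiness will be collected as well as the responses of the patient to the following questions". The two items are "sore throat: absent, mild, moderate, severe" and "cough: absent, mild, moderate, severe". Neither item asks whether the symptom is new or has changed.

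Section 16.1 sets out what happens at each location. For recovery it says "Post-anesthesia care unit where time to discharge readiness, patient cough severity and sore throat severity will be collected". For the pre-procedure unit it mentions consent and "Pre-anesthesia care unit where patient will receive dextromethorphan", but no symptom rating.

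Section 3.1 admits patients with "Diagnosis of pulmonary disease requiring flexible bronchoscopy", and the exclusions in section 3.2 do not remove patients with chronic cough. Stratification (sections 7.4.3 and 8.1) is by procedure type and inpatient or outpatient status, not by cough. The arms are 24, 12 and 12 (section 8.1). The analysis is descriptive: medians, interquartile ranges and percentages (sections 8.3 and 10.7).

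**The concern.** A patient who arrives with moderate cough and leaves unchanged gets the same score as one whose moderate cough began with the procedure. In a population selected partly for lung disease, some of what is tabulated as post-procedure cough may be cough the patient already had.

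This has two consequences. First, a real difference between techniques is diluted, because patients with persisting cough score as coughing whichever technique they receive. Second, with arms this small, a visible difference may only reflect which arm happened to receive more patients who coughed already. The plan has no inferential analysis, so raw percentages by arm will be read directly, with nothing to show whether the arms started alike. Section 2.3 says that a difference, if found, will be used to size a later superiority trial. A misleading difference in cough could carry forward if this endpoint informs that planning.

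**Working it through.** The plan gives no figure to reproduce: section 8.2 marks sample size determination as not applicable. The check is therefore a reading of the documents plus three illustrations.

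**Is a baseline described?** The pre-procedure steps in sections 4.2, 7.1 and 16.1 are eligibility review, consent and dextromethorphan. No section describes a cough or sore-throat rating before the procedure.

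**Chance imbalance.** Inputs: arm sizes from section 8.1; prevalence of pre-existing cough *p*, assumed because the documents do not give it. With X ~ Bin(n₁, p) and Y ~ Bin(n₂, p) independent, the quantity is P(|X/n₁ − Y/n₂| ≥ 0.20), summed exactly. Because counts are whole numbers, the threshold means at least 5 patients for 24 vs 24 (0.20 × 24 = 4.8), at least 3 for 12 vs 12 (0.20 × 12 = 2.4), and at least 5/24 for 24 vs 12.

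| Comparison | p = 0.2 | p = 0.3 | p = 0.4 | p = 0.5 |
|---|---|---|---|---|
| 24 vs 24 (nebulizers pooled) | 0.103 | 0.155 | 0.184 | 0.193 |
| 24 vs 12 | 0.183 | 0.248 | 0.281 | 0.291 |
| 12 vs 12 | 0.197 | 0.263 | 0.297 | 0.307 |

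The values are symmetric about 0.5, so p = 0.7 gives the same as p = 0.3.

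**Dilution.** Suppose a share *q* of patients has persisting prior cough that is scored as present in every arm. Suppose also that, among the rest, cough occurs in 50% with one technique and 20% with another (all assumed). The observed proportions are q + (1 − q) × 0.50 and q + (1 − q) × 0.20, so the observed difference is (1 − q) × 30 points:
- q = 0: 30 points
- q = 0.2: 60% vs 36%, 24 points
- q = 0.4: 70% vs 52%, 18 points
- q = 0.6: 80% vs 68%, 12 points

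**What a baseline would buy.** Let ρ be the correlation between baseline and post-procedure ratings (assumed). Treat the ratings as numeric with equal variances, which is only an approximation for a four-level scale. Relative to the post-procedure rating alone, linear adjustment leaves variance 1 − ρ², and a change score has variance 2(1 − ρ).

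| ρ | Removed by adjustment (ρ²) | Left after adjustment | Change score |
|---|---|---|---|
| 0.3 | 9% | 0.91 | 1.40 |
| 0.5 | 25% | 0.75 | 1.00 |
| 0.7 | 49% | 0.51 | 0.60 |

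A change score is 40% noisier than having no baseline at ρ = 0.3, gains nothing at 0.5, and does worse than adjustment at all three values.

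**The case against.** The strongest reply is that this is a 48-patient feasibility study with descriptive analysis, the endpoint is secondary, and randomization already protects the comparison. Much of that stands. Randomization means that the missing baseline does not favor any arm in expectation. A reader might infer systematic bias from the absence of a baseline, but the documents do not support that.

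It is also fair that section 2.3 frames the question as nebulized against topical. With the two nebulizer arms pooled this is 24 vs 24, the comparison with the smallest chance of imbalance. The figures for arms of 12 apply only when the devices are looked at separately.

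A reader might go further and infer that the primary endpoint suffers because a useful covariate is lost. The documents do not support this either. The plan contains no model for a covariate to enter, and nothing in it links usual cough to cough under general anesthesia that pauses the procedure or needs more anesthetic.

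Nor is the case equally strong for sore throat: lung disease is a reason to expect prior cough, but the documents give no reason to expect prior sore throat.

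Finally, the subject form and the Research Data Plan Review Form are not among the documents, so a baseline item there cannot be ruled out. The supportable statement is that the protocol describes none.

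What survives is narrow: post-procedure cough, as described, cannot distinguish prior from new or worsened cough, and a descriptive plan offers no other way to see whether the arms began alike.

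**Conclusion.** The point holds as a minor, inexpensive improvement to one secondary endpoint. The chance of a baseline gap of at least 20 points is roughly one in six to one in five for the pooled comparison, and about one in four to three in ten when an arm of 12 is involved. These figures assume that 30–50% of patients cough beforehand; at 20% they fall to 10%, 18% and 20% for 24 vs 24, 24 vs 12 and 12 vs 12. The dilution and variance figures rest on assumed contrasts, persistence and correlations, and show scale only. The consequence is noise, dilution and chance imbalance in a randomized comparison. It does not invalidate any planned analysis, and no conclusion about the primary endpoint follows.

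**What to change.** Ask the same four-level cough question in the Pre-Anesthesia Care Unit, before dextromethorphan and before the envelope is opened, so that the answer is free of premedication and knowledge of the assigned arm. The sore-throat question can be added at no real cost. The timing fits the existing schedule: section 7.1 has dextromethorphan given there at least 60 minutes before bronchoscopy, and section 7.4.3 has the envelope opened immediately before the procedure.

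In section 8.3, state that baseline cough will be tabulated by arm and that post-procedure cough will be cross-tabulated by baseline category, summarized as new or worsened versus unchanged or better. With 12 patients in an arm a full four-by-four table will be sparse, so the two-way summary should be specified in advance. If a model is used, include baseline as a covariate. Do not report a raw change score: it can lose precision, it assumes equal spacing between the levels, and patients who start with no cough can only stay the same or worsen.

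If the subject form already carries a baseline item, the protocol need only say so and state how it will be used.

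The cost is one or two extra form fields for each of 48 patients. Sample size, treatment and procedures are unchanged.
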